### 1.2 Per-Protocol (PP) Population

According to the protocol, subject with major protocol violation shall be excluded from PP population. The definition shall be revised to ‘The PP population is defined as the set of patients who meet the ITT population requirements and are not associated with any major protocol violations relevant to efficacy analysis’.

#### 14.1.1.1 9.7.1.2. Per Protocol (PP) Population

The PP population is defined as the set of patients who meet the ITT population requirements and are not associated with any major protocol violations. This population will be identified before the database lock. This population will be used as the supportive analysis population for analysis of the primary and secondary efficacy endpoints.

### 1.3 Treatment Compliance of CX-4945

There is no definition of compliance in the protocol, it's defined as below.

$$\text{Treatment Compliance [%]} = \frac{\text{\# of times of CX-4945 actually administered}}{(\text{Treatment Duration}) * (2 \text{ times of administration/day})} * 100\%$$

Treatment Duration [days] = the last administration date – the first administration + Adjustment

The first administration time	The last administration time	Adjustment
Morning	Morning	+0.5
Morning	Evening	+1
Evening	Morning	+0
Evening	Evening	+0.5

### 1.4 Analysis Method

#### 1.4.1 Inferential Statistics

According to the protocol, no inferential statistics was planned. In the SAP, the inferential testing will be done as appropriate for treatment comparison.

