9.3. SAMPLE SIZE DETERMINATION AND RATIONALE

A total of approximately 20 subjects will be randomized 1:1 in this study. The sample size is based on clinical judgment. No statistical power calculation is used to establish the sample size for this proof-of-concept study.

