9.5. BLINDING

This is an open label study.

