9.8.4. Study Outcome Assessment

For continuous variables data will be summarized by treatment using n, mean, SD, minimum and maximum values. For categorical variables data will be summarized by treatment using frequency and percentage. No inferential statistics are planned. The Safety population will be used for the analysis of safety outcomes.

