### 1.4.2 Method for Time to Event Data

The endpoints about time to event data as below table will be compared between treatment groups by using log-rank test, and corresponding response proportion will be presented by using Kaplan-Meier methods.

- Time to COVID-19-Related Clinical Signs Normalization
- Time to Oxygen Saturation Level Normalization
- Time to moderate COVID-19-Related Symptoms Resolution
- Time to SARS-COV-2 Viral Clearance
- Time to Improvement on NIAID 8-Point Clinical Progression Outcomes Scale (additional analysis, not mentioned in the protocol)
- Time to Improvement on EQ-5D-5L Imaginable Health Status (additional analysis, not mentioned in the protocol)

Considering the early censor on time to response (Normalization / Recovery / Viral Clearance / Improvement) data will result in over optimistic in statistical results, two data estimation methods below will be used for the sensitive analyses. Results will be claimed as robust if the results of both methods are consistent.

Time to Response (days), Best Case Scenario  
= Days to first response for responder,  
= Days to last observation for non-responder (censored)

Time to Response (days), Worst Case Scenario  
= Days to first response for responder,  
= Days to planned last observation date (31 for EQ-5D-5L and SARS-COV-2 Viral Clearance at visit 7, 45 for others at visit 8) for non-responder (censored)

Days to first response = date of first response – the first treatment date/time + 1  
Days to last observation = date of last evaluation – the first treatment date/time + 1  
For Arm SOC, the first treatment date is the date of visit 2

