## 2 Protocol Versions and Protocol Amendments

The first subject was enrolled on 3-Dec-2020, and the last subject is expected to be dismissed on 7-Oct-2021. All applied protocol and CRF versions are listed as below.

No.	Protocol Version	CRF Version	IRB Approval	FDA Approval
1	3.0, 20OCT2020	1.1, 12OCT2021	5-Nov-2020	3-Nov-2020
2	Amendment 1.0, 11MAY2021	1.0, 06SEP2021	24-May-2021	24-Jun-2021

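### The SAP adds between-arm tests to a trial planned without inference, does not label the p-values as descriptive, and gives no effect estimate for the time-to-event and NIAID outcomes

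*SAP*

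**What the plan says.** Protocol 9.8.4 states: "No inferential statistics are planned". Section 9.5 adds: "This is an open label study". Section 9.3 gives the size and its basis: "A total of approximately 20 subjects will be randomized 1:1 in this study" and "No statistical power calculation is used to establish the sample size for this proof-of-concept study". The only primary endpoint is safety.

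SAP 1.4.1 repeats the protocol position and changes it: "In the SAP, the inferential testing will be done as appropriate for treatment comparison". SAP 1.4.2 to 1.4.4 then name log-rank tests for six time-to-event endpoints, t or Wilcoxon tests and ANCOVA for continuous data, and chi-square, Fisher or Mantel-Haenszel tests for categorical and ordinal data. Two of the six time-to-event endpoints are marked as additions, for example "Time to Improvement on EQ-5D-5L Imaginable Health Status (additional analysis, not mentioned in the protocol").

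SAP 1.4.2 defines a best-case and a worst-case scenario for the time-to-event endpoints and sets a rule: "Results will be claimed as robust if the results of both methods are consistent".

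On timing, SAP section 2 says that "the last subject is expected to be dismissed on 7-Oct-2021" and lists CRF versions dated 6-Sep-2021 and 12-Oct-2021.

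**The concern.** A small open-label trial with no lead efficacy endpoint and no alpha can still report its data fairly if it describes them. Once p-values are printed across many endpoints, visits and populations without a label, any value below 0.05 is likely to be read as evidence of benefit. The SAP contains no sentence to prevent that reading, and its robustness rule supplies language that encourages it.

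The problem is sharpest in the time-to-event tables. There the only between-arm result is a log-rank p-value, so the reader would not see how imprecise a comparison of about 10 patients per arm is. What is at stake is what the trial may claim on efficacy, not the safety conclusion: the adverse event tables in SAP 14.3.1 carry no p-value column.

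**Working it through.** The plan has no figure of its own to reproduce: it gives no alpha, power, effect size, SD or event rate. Two-sided 0.05 is assumed below, to match the 95% CIs. The only 0.05 threshold in the SAP is the Shapiro-Wilk check in 3.1.

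**1. Number of efficacy p-values.** Six tables use the time-to-response layout (14.2.1.1, 14.2.1.4, 14.2.2.1, 14.2.3.2, 14.2.4.2, 14.2.5.2). The layout repeats over two scenarios and two populations (ITT and PP): 6 × 2 × 2 = 24.

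The by-visit tables add, counting post-baseline visits and LOCF in both populations:
- RT-PCR conversion: 4 × 2 = 8
- Viral load change: 4 × 2 = 8
- NIAID improvement/progression: 7 × 2 = 14
- EQ-5D-5L change: 2 variables × 4 × 2 = 16

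Total: 24 + 8 + 8 + 14 + 16 = 70, before laboratory tests and vital signs.

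**2. Chance of at least one p < 0.05 with no true effect, if tests were independent.** 1 − 0.95^k gives 26% for k = 6, 71% for k = 24 and 97% for k = 70. The tests are clearly not independent. Both scenarios use the same responders, PP is a subset of ITT, and clinical-signs normalization contains the SpO2 criterion that is also a separate endpoint. These figures show scale only.

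**3. What agreement of the two scenarios shows.** A responder has the same time in both. A non-responder is censored at the last observation (best case) or at the planned last day, 31 or 45 (worst case). The log-rank statistic depends only on who is at risk at each response time. If no non-responder is censored before the last observed response in either scenario, the risk sets and the statistic are identical. The scenarios can diverge materially only through non-responders who leave early. With little early dropout they agree almost by construction.

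**4. Where a between-arm estimate is specified.**

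| Outcome | SAP table | Between-arm estimate with 95% CI |
|---|---|---|
| RT-PCR conversion | 14.2.3.1 | Yes, difference in proportions |
| Viral load change | 14.2.3.1 | Yes, mean or Hodges-Lehmann |
| EQ-5D-5L change | 14.2.5.1 | Yes, mean or Hodges-Lehmann |
| Laboratory tests, including inflammatory markers | 14.3.2 to 14.3.5 (continuous tests) | Yes, LS-mean or Hodges-Lehmann |
| Vital signs, SpO2 | 14.3.8 | Yes, LS-mean or Hodges-Lehmann |
| Six time-to-event endpoints | 14.2 layout | No; a Difference column is headed but no row fills it |
| NIAID improvement/progression | 14.2.4.1 | No; counts and a p-value only |

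**5. What the missing estimates would show.** With d events and 1:1 allocation, the 95% CI for a hazard ratio is the estimate divided and multiplied by exp(1.96 × √(4/d)). For d = 20 (everyone responds) the factor is 2.40, so an observed ratio of 1.0 has a CI of 0.42 to 2.40. For d = 10 it is 3.45. For a risk difference at 10 per arm with both rates at 50%, the half-width is 1.96 × √(0.25/10 + 0.25/10) = 0.44, or 44 points. Assumed rates of 80% and 50% give 30 ± 40 points, that is −10 to +70.

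**6. Timing, conditional on the dates in SAP section 2.** If 7-Oct-2021 is the last patient's Day 60, Day 1 was 59 days earlier, 9-Aug-2021 (6 to 12 August with the ±3-day window). A document citing a CRF of 6-Sep-2021 was then written no earlier than that patient's Day 29 (26 to 32). From first enrolment on 3-Dec-2020, 277 of 308 days (90%) had passed. If neither CRF date is trusted, the approval date of 24-Jun-2021 in the same table still puts the text at least 203 days after first enrolment (203/308 = 66%).

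**The case against.** The SAP is open about what it does. The tests appear in its section on changes from the protocol, with the protocol sentence reprinted, and both added endpoints are marked as absent from the protocol. Neither is a new domain: NIAID improvement and EQ-5D-5L change are protocol secondary endpoints. Only the time-to-event form and the EQ-5D-5L cut-off at 90 are new. The protocol is not uniformly descriptive either. It sets objectives to compare the arms (section 3), foresees covariate adjustment and multiple imputation (9.7.2, 9.7.3), and leaves efficacy detail to the SAP (9.8.4.1). The robustness rule belongs to a sensitivity analysis for censoring, and applies equally to null results. All of this stands. None of it supplies an alpha, a multiplicity rule, a descriptive label or the missing estimates.

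A reader might infer three stronger points that the documents do not support:

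- **That the SAP gives no effect estimates.** It does for five groups of outcomes, as the table above shows.
- **That the tests were chosen after outcomes by arm had been seen.** The SAP's own date is not visible, and nothing shows what its authors had seen. The date table is also inconsistent: it calls 7-Oct-2021 expected beside a CRF dated 12-Oct-2021, and pairs the later CRF version with the older protocol.
- **That late timing broke a rule.** Protocol 9.8 requires only that the SAP be approved before database lock.

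**Conclusion.** The point holds, and the plan should be changed. The SAP adds at least 70 post-baseline efficacy p-values, 24 of them log-rank, to an unpowered open-label trial whose protocol planned no inference. It does not say how those p-values are to be read. Agreement between the two scenarios is weak support for calling a result robust, because they differ only in the censoring of non-responders. The lack of between-arm estimates is confined to the six time-to-event endpoints and NIAID improvement/progression, but these include both added endpoints.

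The 26% figure rests on independence and on an alpha that the SAP does not state; it should not be cited as this trial's error rate. If the dates in SAP section 2 are right, the tests were specified when most open-label follow-up was complete. That is a reason for caution in wording, not a finding of data-driven choice. The SAP sets no efficacy success criterion, so the risk lies in how results are reported.

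**What to change.** 1. In SAP 1.4.1, state that all p-values are nominal, unadjusted for multiplicity and descriptive, and that no efficacy claim rests on them.
2. In SAP 1.4.2, delete the sentence on claiming robustness. Report the two scenarios only as a check of sensitivity to the censoring of non-responders.
3. In the time-to-response layout (SAP 14.2), fill the Difference column with a between-arm estimate and 95% CI. A hazard ratio or a restricted-mean difference would serve; the choice is a matter of preference.
4. In SAP 14.2.4.1, add a risk difference with 95% CI for NIAID improvement and progression.

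The two added endpoints need no further marking as additions, since the SAP already does that. The cost is a few sentences, one row per table and some programming. No new data are needed. The sponsor gives up claims of statistical significance, which the protocol had not planned to make.

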#### 9.8.4. Study Outcome Assessment

For continuous variables data will be summarized by treatment using n, mean, SD, minimum and maximum values. For categorical variables data will be summarized by treatment using frequency and percentage. **No inferential statistics are planned.** The Safety population will be used for the analysis of safety outcomes.

### 1.4.2 Method for Time to Event Data

The endpoints about time to event data as below table will be compared between treatment groups by using log-rank test, and corresponding response proportion will be presented by using Kaplan-Meier methods.

- Time to COVID-19-Related Clinical Signs Normalization
- Time to Oxygen Saturation Level Normalization
- Time to moderate COVID-19-Related Symptoms Resolution
- Time to SARS-COV-2 Viral Clearance
- Time to Improvement on NIAID 8-Point Clinical Progression Outcomes Scale (additional analysis, not mentioned in the protocol)
- Time to Improvement on EQ-5D-5L Imaginable Health Status (additional analysis, not mentioned in the protocol)

Considering the early censor on time to response (Normalization / Recovery / Viral Clearance / Improvement) data will result in over optimistic in statistical results, two data estimation methods below will be used for the sensitive analyses. Results will be claimed as robust if the results of both methods are consistent.

Time to Response (days), Best Case Scenario  
= Days to first response for responder,  
= Days to last observation for non-responder (censored)

Time to Response (days), Worst Case Scenario  
= Days to first response for responder,  
= Days to planned last observation date (31 for EQ-5D-5L and SARS-COV-2 Viral Clearance at visit 7, 45 for others at visit 8) for non-responder (censored)

Days to first response = date of first response – the first treatment date/time + 1  
Days to last observation = date of last evaluation – the first treatment date/time + 1  
For Arm SOC, the first treatment date is the date of visit 2

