9.4. RANDOMIZATION

The randomization will use block size of 2 or 4 with a 1:1 ratio of CX-4945 in addition to SOC group and SOC alone group to ensure balanced distribution of subjects. An individual, independent

of the clinical trial team, will develop the randomization schedules. Subjects who have provided written informed consent and have met all the inclusion criteria and none of the exclusion criteria will be randomized to one of the treatment groups.

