## (5) Efficacy Endpoints:

- **Time to COVID-19-Related Clinical Signs Normalization: Normal when all below are met**
  - (1) Fever is <36.6°C from axillary site, or < 37.2°C from oral site, or < 37.8°C from rectal or tympanic site, or <37.2°C from forehead by using non-contact infrared thermometers
  - (2) Respiratory rate is < 20 bpm while breathing room air
  - (3) SpO2 ≥ 96% in room air without shortness of breath or dyspnea caused by COVID-19
  - (4) Heart rate < 90 beats per minute

If some signs listed above were caused by other conditions documented in the medical history and started before COVID-19, the patient can be considered as recovered, when these signs return to the previous (pre-COVID-19) values
- **Oxygen Saturation Level Normalization: Normal when SpO2 ≥ 96%**
- **Resolution of moderate COVID-19-Related Symptoms when all below are met:**
  - No key COVID-19-related symptoms scored higher than 1.
  - If some symptoms were caused by other conditions documented in the medical history and started before COVID-19 (e.g, insomnia), the patient can be considered as recovered, when these symptoms return to the previous (pre-COVID-19) value.
- **SARS-CoV-2 Viral Clearance: negative RT-PCR**

- **NIAID 8-Point Clinical Progression Outcomes Scale:**
  - 1 - Death
  - 2 - Hospitalized, on invasive mechanical ventilation or extracorporeal membrane oxygenation (ECMO)
  - 3 - Hospitalized, on non-invasive ventilation or high flow oxygen devices
  - 4 - Hospitalized, requiring supplemental oxygen
  - 5 - Hospitalized, not requiring supplemental oxygen - requiring ongoing medical care (COVID-19 related or otherwise)
  - 6 - Hospitalized, not requiring supplemental oxygen - no longer requires ongoing medical care
  - 7 - Not hospitalized, limitation on activities and/or requiring home oxygen
  - 8 - Not hospitalized, no limitations on activities
- **EQ-5D-5L Imaginable Health Status Improvement: Imaginable Health Status <90 at baseline and ≥ 90 after baseline**
- **Time to Response (Normalization / Resolution / Viral Clearance / Improvement)**

Time to Response (days), Best Case Scenario  
 = Days to first response for responder,  
 = Days to last observation for non-responder (censored)

Time to Response (days), Worst Case Scenario  
 = Days to first response for responder,  
 = Days to planned last observation date (31 for EQ-5D-5L and SARS-COV-2 Viral Clearance at visit 7, 45 for others at visit 8) for non-responder (censored)

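### Agreement of the SAP's best and worst case is not enough to claim robustness: both treat the two arms' early non-responders alike, and with losses on SOC the worst case shifts towards CX-4945

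*SAP*

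**What the plan says.** SAP 1.4.2 lists six time-to-response endpoints that "will be compared between treatment groups by using log-rank test", with Kaplan-Meier response proportions. It is concerned that early censoring may make results look too good, and so "two data estimation methods below will be used for the sensitive analyses". A responder's time is the same under both methods. They differ only for a patient with no recorded response:

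- **Best case:** "Days to last observation for non-responder (censored"), which is ordinary censoring.
- **Worst case:** censored at the planned last day (Day 31 for viral clearance and EQ-5D-5L, Day 45 for the rest), so the patient stays in the risk set as a non-responder.

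The Efficacy Endpoints item of the SAP's instructions repeats both rules. Neither place distinguishes the arms. SAP 1.4.2 then fixes the claim: "Results will be claimed as robust if the results of both methods are consistent". It does not define consistent.

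Three other sections matter. Protocol 9.7.3 planned multiple imputation for efficacy. SAP 1.5 drops it as unrealistic at this sample size and adds LOCF for by-visit analyses only. SAP 1.4.1 adds significance testing, which Protocol 9.8.4 had excluded.

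**The concern.** This pair of scenarios is the only missing-data check on the log-rank endpoints, and the SAP attaches a public claim to it. A sensitivity analysis of a treatment comparison should ask what happens if the missing outcomes differ between the arms. This one varies the assumption in both arms together.

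Worst case is also a misleading name for a comparison. It is the worst case for each arm's response curve. For the difference between arms, it penalises whichever arm lost more patients. If that arm is SOC, the worst case strengthens an apparent CX-4945 benefit, and the check cannot count against the drug.

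Unequal loss is possible. Protocol 9.5 says "This is an open label study", and control patients receive no study drug. Protocol 9.3 says "A total of approximately 20 subjects will be randomized 1:1 in this study", so two or three patients can decide a result. At stake is whether a report may call a CX-4945 benefit robust when a few unobserved SOC recoveries would remove it.

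**Working it through.** **Inputs from the documents.** About 20 patients randomised 1:1 (Protocol 9.3, 9.4); open label (9.5); log-rank test and the two censoring rules (SAP 1.4.2); visits on Days 4, 8, 11, 14, 28 and 45 after Day 1 (Protocol 3). There is no planned figure to reproduce: "No statistical power calculation is used to establish the sample size for this proof-of-concept study", and no dropout rate is given.

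**Assumptions, none in the documents.** Exactly 10 per arm; two-sided 0.05; consistent means the same direction and the same significance verdict. For the simulation: exponential response times read at the next visit, and dropouts last seen on Day 1, 4 or 8, unrelated to outcome.

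**Step 1. Why the worst case moves as it does.** With d responses at an event day, and n_A (CX-4945) and n_B (SOC) at risk, n = n_A + n_B:

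- E = Σ d·n_A/n
- V = Σ d·n_A·n_B·(n−d)/(n²(n−1))
- z = (O−E)/√V, positive when CX-4945 responds faster.

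Keeping SOC dropouts in the risk set raises n and leaves n_A alone, so E falls and O−E rises.

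**Step 2. Worked example.** CX-4945 responses on Days 4, 4, 8, 8, 8, 11, 11, 14, 14, 28. SOC responses on Days 8, 11, 14, 28, 28, 28, one patient without response at Day 45, and three dropouts last seen on Day 4. In the crossed set those three respond at their next visit, Day 8.

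| Day | Responses A/B | Best: at risk A/B, E | Worst: at risk A/B, E | Crossed: at risk A/B, E |
|---|---|---|---|---|
| 4 | 2/0 | 10/10, 1.000 | 10/10, 1.000 | 10/10, 1.000 |
| 8 | 3/1 (crossed 3/4) | 8/7, 2.133 | 8/10, 1.778 | 8/10, 3.111 |
| 11 | 2/1 | 5/6, 1.364 | 5/9, 1.071 | 5/6, 1.364 |
| 14 | 2/1 | 3/5, 1.125 | 3/8, 0.818 | 3/5, 1.125 |
| 28 | 1/3 | 1/4, 0.800 | 1/7, 0.500 | 1/4, 0.800 |

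- Best: (10 − 6.422)/√2.513 = 2.26, p = 0.024.
- Worst: (10 − 5.167)/√2.596 = 3.00, p = 0.003.
- Crossed: (10 − 7.400)/√2.849 = 1.54, p = 0.12.

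The SAP's rule calls this result robust. Three SOC recoveries one visit later would remove its significance, and the two SAP scenarios do not bracket that outcome.

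**Step 3. No true effect** (medians 10 v 10 days, 3,000 trials per setting). Share with p<0.05 favouring CX-4945, against 2.5% nominal:

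| Dropout, CX-4945 v SOC | Best | Worst | Both |
|---|---|---|---|
| 0% v 30% | 2.7% | 16% | 2.7% |
| 10% v 40% | about 2% | about 15% | about 2% |

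With losses only on SOC, the worst case removes none of the best case's false positives.

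**Step 4. True effect** (medians 5 v 15 days). Among results favouring CX-4945 with p<0.05 under both methods, the share losing p<0.05 when CX-4945 dropouts never respond and SOC dropouts respond at the next visit:

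| Dropout, CX-4945 v SOC | Share lost |
|---|---|
| 0% v 10% | 16% |
| 10% v 10% | 25% |
| 20% v 20% | 54% |
| 10% v 30% | 60% |
| 30% v 0% | 0% |

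Simulation error on these shares is about 1 to 2 percentage points.

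**Step 5. Range.** With dropout last seen as late as Day 11, 4,000 trials, medians of 6 v 12 or 5 v 15 days, and loss counted under either arm-differential scenario, the share is 49 to 54% at 20% v 20%, 42 to 50% at 0% v 30%, and 0 to 0.4% at 30% v 0%.

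**The case against.** The strongest defence is that the pair does the job the SAP gives it. It tests one named departure, that dropouts never respond, in order to counter optimism from early censoring. When losses are on CX-4945, the worst case is the bound against the drug, and no robust result was lost at 30% v 0%. The two methods also disagree in 14 to 39% of simulated trials with a true effect and at least 10% dropout in one arm, so the label can be withheld. All of this stands. A reader might infer that the pair is no test of missing data at all; that goes too far.

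A reader might also take the 16% as the rule's false-positive rate. It is the rate for the worst case alone. The claim needs both methods to agree, and the joint rate was 1.0 to 2.7% in the null settings with 20% v 20%, 0% v 30% and 10% v 40% dropout.

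Nor is it shown that both scenarios lean towards CX-4945. With dropout unrelated to outcome, the best case has a mean z of about zero. A lean in both would need outcome-related dropout, which was not simulated.

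Dropout may also be low. Protocol 4.3 and 7.1 keep patients who stop therapy in follow-up. A patient already recorded as recovered counts as a response, so leaving later changes nothing for that endpoint. This limits the problem without removing it: Protocol Table 1, footnote 14, allows recovered patients remote follow-up, and a remote Day 28 visit may yield no swab for viral clearance.

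Finally, the arm-differential scenario is deliberately extreme, and many real effects in a trial of 20 would fail it. It therefore serves as a bound, not as the expected truth. The affected endpoints are secondary or additional; the primary endpoint is safety.

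**Conclusion.** The concern holds in a limited form. Agreement between the two scenarios shows consistency under common censoring rules. It is not sufficient to call a treatment comparison robust to missing data, because neither scenario varies the assumption by arm. With losses only on SOC, the worst case adds no protection beyond the best case.

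The direction follows from the log-rank formula and needs no assumed rates. The size does: under the stated assumptions, 16 to 60% of robust results lose p<0.05 across the settings with any SOC dropout, and 0% when only CX-4945 patients drop out. With no early loss the methods essentially coincide. That is not a defect, but the word robust then carries no information. The point is worth correcting because the SAP commits to a claim; the documents do not show that the rule raises the false-positive rate.

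**What to change.** Replace the robustness sentence in SAP 1.4.2 with:

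> Agreement of the two scenarios will be reported as consistency under common censoring rules. Early non-responders will be counted by arm. Two arm-differential scenarios will be presented as bounds: CX-4945 early non-responders kept as non-responders to the planned last day with SOC early non-responders responding at the next scheduled visit, and the reverse. A result will be described as robust to missing data only if its direction and significance verdict hold across these bounds; otherwise the scenario in which it changes will be stated.

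Where nobody leaves early, state that no missing-data sensitivity analysis was needed. A tipping-point analysis, or deleting the robustness sentence, would also meet the concern.

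The cost is SAP wording and two extra runs per endpoint, with no change to trial conduct. The downside is that fewer results can be described as robust.

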### 1.1 Visit Adjustment

Visit 6 is End of Treatment (EOT) Visit, Treatment Discontinuation Visit or Early Withdrawal Visit at/before EOT. Data of visit 6 not in its visit window will be shifted to corresponding scheduled visit for analysis as in table below (marked ‘\*’). Visit name will be presented as ‘Adjusted Visit’ for the visits reallocated to its original scheduled visit or the next visit after preceding scheduled visit.

	Visit 6 to Visit 3~6
COVID-19-Related Symptoms	*
Clinical Status - NIAID 8-Point Clinical Progression Outcomes Scale	*
Laboratory Examination	*
Vital Signs, Pulse Oxygen Saturation (SpO2) and COVID-19-Related Clinical Signs	*

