## 14.2 EFFICACY DATA

### <TTR Layout: For Time to Response Data>

Population: Intent-to-Treat Population / Per-Protocol Population

Characteristics	Treatment Group	Difference	P-value
--Repeat Population: <See populations above>			

- Variable per table title:

Time to COVID-19-Related Clinical Signs Normalization [days]

Time to COVID-19-Related Symptoms Resolution [days]

[figure not shown]
Time to SARS-COV-2 Viral Clearance [days]

. Repeat Scenario: Best Case Scenario, Worst Case Scenario

N (Missing)	XXX (XXX)	LOGRANK
Censored No.	XXX (XXX%)	0.XXXX
Observed No.	XXX (XXX%)	
Q1 [95% CI]	XXX [XX~XX]	
Median [95% CI]	XXX [XX~XX]	
Q3 [95% CI]	XXX [XX~XX]	
Mean (SE)	XXX (XXX)	
Min	XXX	
Max (Observed)	XXX	
Max	XXX	

*Footnote the definition according to [Instructions and Abbreviations] of title pages.*

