### 14.2.1.2 Figure of Normalization Proportion on COVID-19-Related Clinical Signs (Best Case Scenario)

### 14.2.1.3 Figure of Normalization Proportion on COVID-19-Related Clinical Signs (Worst Case Scenario)

*Use TTR Figure Layout*

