### 14.2.1.5 Figure of Normalization Proportion on Oxygen Saturation Level (Best Case Scenario)

### 14.2.1.6 Figure of Normalization Proportion on Oxygen Saturation Level (Worst Case Scenario)

*Use TTR Figure Layout*

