### 14.2.2.2 Figure of Recovery Proportion on COVID-19-Related Symptoms (Best Case Scenario)

### 14.2.2.3 Figure of Recovery Proportion on COVID-19-Related Symptoms (Worst Case Scenario)

*Use TTR Figure Layout*

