### 14.2.4.3 Figure of Improvement Proportion on NIAID 8-Point Clinical Progression Outcomes Scale (Best Case Scenario)

### 14.2.4.4 Figure of Improvement Proportion on NIAID 8-Point Clinical Progression Outcomes Scale (Worst Case Scenario)

*Use TTR Figure Layout*

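### The worst-case analysis censors non-responders at Day 45 although Visit 8 may fall as late as Day 48, so the worst-case response curve can end above the best-case curve.

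*SAP*

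**What the plan says.** SAP 1.4.2 compares the arms by log-rank test and presents Kaplan-Meier response proportions. Because early censoring can make results look too good, it defines two scenarios and will call a result robust if both are consistent. Responders take their actual day of first response in both. Non-responders are censored at their actual last evaluation in the best case and at a fixed planned day in the worst case: "31 for EQ-5D-5L and SARS-COV-2 Viral Clearance at visit 7, 45 for others at visit 8) for non-responder (censored". Instructions (5) repeats the rule: "45 for others at visit 8) for non-responder (censored".

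The visit table in Instructions (4) gives Visit 7 as Day 28 ± 3 and Visit 8 as Day 45 ± 3.

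The only re-dating of visits is in SAP 1.1 and concerns Visit 6: "Data of visit 6 not in its visit window will be shifted to corresponding scheduled visit for analysis".

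The layout in SAP 14.2 reports both scenarios, with quartiles, for each endpoint ("Repeat Scenario: Best Case Scenario, Worst Case Scenario"). Worst-case figures are planned for all four endpoints that run to Visit 8: clinical signs (14.2.1.3), oxygen saturation (14.2.1.6), symptoms (14.2.2.3) and NIAID improvement (14.2.4.4).

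**The concern.** The two fixed days do not follow one rule. Day 31 is the last day of the Visit 7 window, whereas Day 45 is the middle of the Visit 8 window. A non-responder whose Visit 8 falls on Day 46, 47 or 48 is therefore censored earlier in the worst case than in the best case, which is the reverse of what a worst case should do.

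The worst-case risk set after Day 45 contains only patients who go on to respond, so any late response takes that arm's curve to 100%. A reader of the tables and figures could see a worst-case final proportion, or a third quartile, that looks better than the best-case one. The penalty meant for early dropouts also disappears from the tail. Agreement or disagreement between the scenarios is the SAP's robustness criterion, and here it could come from the cut-off day alone.

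**Working it through.** **1. Do the stated days match the visit table?** (SAP Instructions (4); the first treatment day counts as Day 1, SAP 1.4.2.)

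| Rule | Visit 7 | Visit 8 |
|---|---|---|
| Stated in SAP 1.4.2 | 31 | 45 |
| End of window | 28 + 3 = 31 (match) | 45 + 3 = 48 (no match) |
| Nominal day | 28 (no match) | 45 (match) |

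No single rule gives both values. The +1 in the day count does not explain the gap.

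**2. Effect on the Kaplan-Meier curve.** Response by day t is 1 − Π(1 − d/n), where d is the number of first responses on a day and n the number still at risk. Arms of 10 are used, since the protocol (9.3) plans about 20 patients randomized 1:1. The response patterns are invented for illustration.

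*Example 1.* 8 respond by Day 28, one on Day 47, one non-responder is seen on Day 48. Response at Day 45 is 80%.
- Best case, and worst case with 48: n = 2 on Day 47, so 1 − 0.2 × 1/2 = 90%.
- Worst case with 45: n = 1, so 1 − 0.2 × 0 = 100%.

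*Example 2.* 6 respond by Day 28, one on Day 47, three non-responders are seen on Day 48. Response at Day 45 is 60%.
- Best case, and worst case with 48: n = 4, so 1 − 0.4 × 3/4 = 70%. Q3 (the day 75% is passed) is not reached.
- Worst case with 45: n = 1, so 100%. Q3 is Day 47.

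*Example 3.* As Example 2, but two of the three non-responders drop out on Day 8, after three of the six early responses.
- Best case: 1 − 0.7 × 2/5 = 72% at Day 45; then n = 2, so 1 − 0.28 × 1/2 = 86%.
- Worst case with 45: 60% at Day 45, then 100%.
- Worst case with 48: 60% at Day 45, then 1 − 0.4 × 3/4 = 70%.

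The dropout penalty is intact at Day 45 (72% against 60%) and is lost afterwards. Q3 is Day 47 in both the best case and the worst case with 45, and is not reached with 48.

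**3. When does inversion occur?** An arm needs a first response on Day 46 to 48 and at least one non-responder last seen on or after that day. If all its non-responders were last seen earlier, both curves reach 100% and there is no inversion at that point. Up to Day 45 the worst-case curve is never the higher one.

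**4. Log-rank test, a constructed example without dropouts.** Arm 1 responds on Days 4, 8, 8, 11, 14, 46, 47 and 47, with two non-responders seen on Day 48. Arm 2 responds on Days 8, 11 and 14, with seven non-responders seen on Day 48. The statistic is (O − E)²/V for Arm 1, with O = 8.
- Best case, and worst case with 48: E = 4.797, V = 2.486, so (3.203)²/2.486 = 4.13, p = 0.042.
- Worst case with 45: E = 6.653, V = 1.826, so (1.347)²/1.826 = 0.99, p = 0.319.

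**5. How often? Simulation on assumed inputs.** 10 per arm, no treatment difference, exponential response times with median 10 days, 15% never responding, visit days uniform within their windows, dropout on Day 4 to 14, six dropout patterns from 0 to 40% per arm, 3,000 trials each.

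| Result | Share of trials |
|---|---|
| Worst above best in at least one arm, rule of 45 | 16.0 to 25.0% |
| The same, at or before Day 45 | 0% |
| The same, rule of 48 | 0% |
| Worst-case Q3 differs between 45 and 48 in at least one arm | 17.6 to 28.6% |
| Two-sided log-rank verdict differs between 45 and 48 | 1.2 to 3.0% |

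Sensitivity at 10% dropout, with medians of 3 to 20 days and 5 to 30% never responding: inversion in 0.1 to 46.3% of trials (2.3 to 38.3% for medians of 5 to 14 days). If half of all visits fall on the nominal day: 6.9 to 8.0%. If no Visit 8 falls after Day 45: 0%.

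**The case against.** The arithmetic is not in dispute. The strongest objections concern its weight.

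- **The trigger is narrow.** The patient must still be a non-responder through Visit 7 and first respond at a Visit 8 held after Day 45, with a persistent non-responder in the same arm seen that day or later. The SAP worries about early censoring, and its rule handles that correctly through Day 45. This stands as a limit on size.
- **The frequencies rest on inputs the documents do not give.** With a 5-day median instead of 10, inversion falls to about 4% of trials; with half of visits also on the nominal day, to about 1%. This stands: the percentages are illustrative, and only the mechanism is certain.
- **Example 3 depends on when the early responses occur.** If none to all six precede the Day 8 dropouts, the best case at Day 45 runs from 75% down to 60% and its final value from 87.5% to 80%. The 100% and 70% worst-case values do not change.
- **Little hangs on it.** These are secondary or additional endpoints in a trial of about 20 patients with no power calculation, and the primary endpoint is safety. Oxygen saturation is probably less exposed, because Protocol 5.1.2 excludes values of 93% or lower at entry. This also stands.
- **The planned observation day may simply mean the nominal day.** Then 45 is right and 31 is the odd value. But the matching Visit 7 value would be 28, and the same inversion could occur there on Days 29 to 31. That reading moves the inconsistency without removing it.

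**Conclusion.** The concern holds. As written, the worst-case rule for the four Visit 8 endpoints can give a non-responder a shorter time than the best-case rule, and any first response on Day 46 to 48 takes that arm's worst-case curve to 100%. In the examples the final proportion is overstated by 10 to 30 percentage points relative to a cut-off of Day 48.

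The mechanism follows from the SAP alone and is certain. Its frequency is not: on assumed inputs it ranges from 0% when no Visit 8 is late to 46.3% in the least favourable setting tried. The damage is confined to the tail after Day 45. EQ-5D-5L and viral clearance are not affected when Visit 7 is in window. The point should be corrected because it undermines the comparison on which the SAP bases its claim of robustness, but it does not threaten the trial's main conclusions.

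**What to change.** In SAP 1.4.2 and in Instructions (5), replace 45 by 48, or the actual last observation day if that is later. For the Visit 7 endpoints, keep 31 and add the same clause. Every non-responder's worst-case time is then at least as long as the best-case time, so the risk set on each response day is at least as large and the worst-case curve cannot exceed the best-case curve on any day.

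One gap remains. If a first response is recorded out of window, after Day 48, dropouts censored at 48 have already left the risk set and their penalty is again lost, although the curves still cannot invert. If such visits occur, a single common day for all non-responders, no earlier than the last observation in either arm, would close it.

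The cost is one number and one clause, in two places. No new data or extra analyses are needed, and curves up to Day 45 do not change.
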